#### **10.3.1. Definition of the populations**

The following populations will be studied:

- The Intent to Treat population (ITT) is defined as all patients who received at baseline the allocated studied procedure and for whom a documented ulcer status (at minimum closed or not closed ulcer) is available at least one time after the inclusion of the patient.
- The Per Protocol population (PP) consists of all ITT patients, for whom no major protocol deviations were observed, and have been treated with the allocated procedure for a minimum of 4 weeks.
- The Safety population is defined as all included and treated patients (at least one documented application of studied systems).

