## 5. STUDY CONDUCT

### 5.1. Synoptic diagram of the investigation

For all included patients, the scheduled treatment duration is 12 weeks. Patients will be allocated to the Urgo K2 compression system and a wound dressing from the UrgoStart® range. Both devices must be applied according to manufacturers' recommendations as described in the respective device monographs (Appendix 1&2).

After obtaining the patient's written consent to participate and once all inclusion and exclusion criteria are met, patients will be included in the study. Patients will then be seen at Week 2 and Week 4 ± 3 days during the first month, and then every four weeks, until the 12th week for wound assessment or until complete wound closure if it happens before, with all the visits being documented in the case report form (CRF).

At each of these visits, the investigator will perform a clinical assessment and will measure the wound with a ruler, and will also take a photographic record of the venous leg ulcer.

The treatment may be discontinued, temporarily or definitively, before the required 12 weeks have been completed if the investigator deems this to be necessary: this must be then documented in the Case Report Form (CRF).

A temporary discontinuation of the tested treatment (compression system or the primary dressing) must not exceed 2 weeks; after this time, it will become a permanent discontinuation.

In case of permanent discontinuation, the investigator has to follow-up the patient until Week 12, as expected in the protocol and to treat him at his entire convenience.

The acceptability of the study treatment will also be assessed at each visit planned in the protocol.

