#### **1.2.5. Photographic record**

Photographs will be taken by the investigator at baseline and at every visit planned in the protocol till the end of the treatment period (Week 12 or before, if withdrawal or healing occurred), according to the investigator's normal procedures.

A ruler will be used when taking the photographic records.

At the end of this Inclusion visit, the investigator will give the Patient a letter for the nurse who will provide the care in the community, between two visits planned in the protocol. This letter will inform the community HCP about the study and will provide recommendations on how to use the products which are under evaluation.

The investigator, at the end of the inclusion visit, will give the patient an appointment for the next visit planned in the protocol, two weeks after the current one.

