### **5.3. INTERMEDIATE ASSESSMENT**

Over the 12 weeks of follow-up, intermediate assessments will be performed at the following frequency: W2, W4 and W8.

A period of two week is defined as 14 days ( $\pm 2$  days), which means that:

- W2 is between the 12th and the 16th day of treatment,
- W4 is between the 26th and 30th day of treatment,
- W8 is between the 54th and 58th day of treatment.

At each visit planned in the protocol, the investigator will note the following in the Case Report Form:

- The characteristics of the lesion (if this one is still present),
- The occurrence of any local adverse event (LAE),

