#### **5.4. ASSESSMENT IN THE EVENT OF STUDY WITHDRAWAL BEFORE W12**

A premature study withdrawal may occur for any of the following reasons:

- Withdrawal of informed consent,
- Healing of the tested wound; thus, the patient will have to consult the investigator as soon as possible after the onset of the wound closure to document the event and provide the exact date of the closure,
- Onset of a local adverse event requiring permanent discontinuation of the tested treatment,
- Intercurrent adverse event requiring withdrawal,
- Any other reason, to be documented.

A temporary discontinuation of the study treatment must not exceed two weeks; if it does so, it becomes a permanent discontinuation.

**In case of permanent discontinuation of the treatment (studied compression system or the interactive dressing whatever), the investigator is asked to perform the planned protocol evaluations, at the same frequency, until the final evaluation (Week 12), whatever any local treatment applied.**

On the day of permanent discontinuation, the investigator is asked:

- To make a clinical assessment,
- To measure the study lesion with a ruler,
- To make a photographic record,
- To measure the ankle circumference, in order to follow the evolution of any oedema of the lower limb, if existing.

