## 6. ASSESSMENT CRITERIA

### 6.1. MAIN CRITERION

The main judgment criterion is the completely closed study ulcer (100% re-epithelialization) evaluated at last available study visit (12 weeks, at the latest).

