### 6.2. SECONDARY CRITERIA

The secondary criteria are to assess or to measure the:

- Time to reach complete wound closure,
- Relative and Absolute wound surface area reduction ( $\text{area}_{t0} - \text{area}_{t\text{last}}$ ),
- Percentage of patients with a  $\geq 30\%$  wound area reduction  $[(\text{area}_{t0} - \text{area}_{t\text{last}}) / \text{area}_{t0} * 100]$  at Week 4,
- Evolution of the ankle circumference,
- The Patient Quality of Life through a specific the WoundQuol Questionnaire,
- The safety of the procedure (nature and number of emergent local adverse events),
- Patients' acceptability to the studied procedure (compression system and dressing) evaluated by the investigator and by the patient,
- The dressing change frequency.

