#### **10.3.2. STUDIED PATIENTS / SUBJECTS**

##### **Disposition of patients / subjects**

The number of included patients, the number of patients who completed the planned medical visits and the number of patients who completed the overall study will be tabulated. The number of patients who discontinued prematurely the study will be also described.

Moreover, discontinued patients will be listed giving patient's number, age at inclusion, gender, last compression received, and reason for withdrawal and study duration.

A Subgroup analysis will be performed considering the ankle circumference (18-25cm group and 25-32cm group).

**Protocol deviations**; these will be listed by patient.

Moreover, the number of patients with at least one protocol deviation and the number of deviations will be tabulated by category and by term.

**Patients Demographic and other baseline characteristics** will be summarized using descriptive statistics. This analysis will be performed on Safety Population, ITT and PP populations (if different).

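### The Per Protocol set requires 4 weeks of treatment with no exception for earlier closure, so compliant patients who heal before week 4 are dropped because they healed (minor wording fix)

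*Protocol*

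**What the plan says.** Section 10.3.1 of the Protocol defines PP as those ITT patients "for whom no major protocol deviations were observed, and have been treated with the allocated procedure for a minimum of 4 weeks". The two conditions are joined by *and*, so both must be met. No exception for closure appears there or elsewhere in the Protocol.

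Several sections treat healing as an end point of treatment or follow-up:

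- Section 5.1 runs the visits to week 12 "or until complete wound closure if it happens before".
- Section 1.2.5 (within the inclusion visit, 5.2) has photographs taken "till the end of the treatment period (Week 12 or before, if withdrawal or healing occurred", so the treatment period can end at healing.
- Section 5.4 gives this as one of the reasons for premature withdrawal: "Healing of the tested wound; thus, the patient will have to consult the investigator as soon as possible". It also asks for the exact closure date.

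The main criterion in section 6.1 is "the completely closed study ulcer (100% re-epithelialization) evaluated at last available study visit (12 weeks, at the latest". Section 6.2 adds "Time to reach complete wound closure" as a secondary criterion.

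On the use of PP, section 10.3.2 says of the baseline description: "This analysis will be performed on Safety Population, ITT and PP populations (if different". Section 10.3.1 says in general terms that the three populations will be studied, but no section assigns an efficacy result to PP. Section 10.1 rules out statistical tests.

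**The concern.** A PP set should exclude patients who did not receive the planned procedure. Here it also excludes patients who followed it exactly and reached the primary outcome early. Membership then depends on the outcome being measured.

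Dropping unhealed patients who stop treatment before week 4 is ordinary PP practice and is not in question.

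At stake is any efficacy summary presented for PP. Its closure rate would be calculated without the fastest successes, and its time to closure would have essentially no values below 4 weeks. A reader would normally take PP to show how the procedure performs when used as planned, and this set would not show that.

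**Working it through.** **Step 1. Can a compliant patient fail the 4-week condition by healing?**

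- The first follow-up visit is at days 12–16 (section 5.3), so closure can be documented well before week 4. Section 5.4 also asks a patient who heals to be seen as soon as possible.
- Once closure is documented, sections 5.1, 5.4 and 1.2.5 end the visits, participation or treatment period. Nothing provides for study treatment to continue on a closed ulcer. Section 5.5 describes a week-12 assessment for all included patients, but an assessment does not lengthen treatment.
- Such a patient is in ITT (treated, with a documented ulcer status), is a success under section 6.1, and has under 4 weeks of treatment. The patient is therefore outside PP.

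**Step 2. What does 4 weeks mean?** Section 5.3 states "A period of two week is defined as 14 days", plus or minus 2 days, and places the week-4 visit at days 26–30. Section 5.1 allows plus or minus 3 days, that is days 25–31. A closure documented at an on-time visit on day 26 or 27 fails a 28-day minimum but passes if the visit window is applied. Section 10.3.1 does not say which is meant.

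**Step 3. Size.** The Protocol has no figure to reproduce: it gives no expected 12-week closure rate, no number of early closures and no number of early stoppers. All counts below are assumed, except N = 60 (sections 1 and 10.1). All 60 are taken to be in ITT, with no other PP exclusions.

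Let c = closures by week 12, k = closures before week 4, and u = patients who stop before week 4 and are unhealed at their last visit.

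- ITT rate = c/60
- PP rate as written = (c − k)/(60 − k − u)
- PP rate with a closure exception = c/(60 − u)

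| c | k | u | ITT | PP as written | PP with exception |
|---|---|---|---|---|---|
| 36 | 0 | 0 | 60.0% | 36/60 = 60.0% | 36/60 = 60.0% |
| 36 | 3 | 0 | 60.0% | 33/57 = 57.9% | 36/60 = 60.0% |
| 36 | 6 | 0 | 60.0% | 30/54 = 55.6% | 36/60 = 60.0% |
| 36 | 3 | 2 | 60.0% | 33/55 = 60.0% | 36/58 = 62.1% |
| 36 | 3 | 10 | 60.0% | 33/47 = 70.2% | 36/50 = 72.0% |
| 18 | 3 | 0 | 30.0% | 15/57 = 26.3% | 18/60 = 30.0% |
| 18 | 3 | 10 | 30.0% | 15/47 = 31.9% | 18/50 = 36.0% |
| 45 | 3 | 0 | 75.0% | 42/57 = 73.7% | 45/60 = 75.0% |
| 45 | 3 | 5 | 75.0% | 42/52 = 80.8% | 45/55 = 81.8% |

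**Step 4. Direction.** With u = 0, each early closure removes one success from numerator and denominator, so the PP rate falls whenever some patients do not close. With u > 0, the removal of unhealed stoppers pushes it up. Setting (c − k)/(60 − k − u) = c/60 gives u = k(60 − c)/c. For c = 36 and k = 3 this is 3 × 24/36 = 2, the row where the two effects cancel. A PP rate equal to ITT would therefore not show that the exclusions were harmless.

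**The case against.** The strongest objection is that no planned result is shown to be affected. The Protocol assigns PP only to baseline characteristics, and only if the sets differ. It plans no test, and which set goes with which endpoint is commonly settled in the SAP. The ITT result keeps every early healer with a documented status. The listing of discontinued patients by reason and study duration (section 10.3.2) would let a reader trace them. This stands, and it is why the point is minor. It does not remove the fault, because the definition is fixed in the Protocol and a listing does not put anyone back into PP.

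Second, every count in the illustration is assumed, and with no early closures and no early stoppers there is no effect. That is also right: the table shows what the rule can do, not what it will do.

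Third, the remedy is not neutral. With the exception, patients with under 4 weeks of treatment enter PP only if they healed, so the PP rate stays the same or rises. Where the two effects would have cancelled, it moves above ITT, for example from 60.0% to 62.1%. This is a real cost. It is acceptable if PP is shown beside ITT with the exclusions counted.

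Fourth, the day 26–27 ambiguity matters only for closures on those days, and the closure exception already resolves them. This is largely correct. Defining the cut-off remains worthwhile because sections 5.1 and 5.3 give different windows.

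**Conclusion.** The point holds and is minor. The conclusion about the definition rests only on reading section 10.3.1 against sections 5.1, 5.4, 1.2.5 and 6.1: as worded, PP excludes compliant patients because they reached the primary outcome early. It needs no assumed numbers.

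The size does rest on assumptions. With three early closures and no early stoppers, the PP closure rate is 1.3 points below ITT when ITT is 75.0%, 2.1 points below at 60.0% and 3.7 points below at 30.0%. Once unhealed early stoppers are also dropped, PP can lie below, at or above ITT, so no net direction can be claimed. The ITT result for the main criterion is untouched.

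**What to change.** In section 10.3.1, extend the duration condition so that it is met by at least 4 weeks on the allocated procedure, *or by treatment until documented complete closure of the study ulcer, if earlier*. State whether 4 weeks means 28 days or the week-4 visit window. If the window is meant, reconcile the plus or minus 3 days in section 5.1 with the plus or minus 2 days in section 5.3 first. If any efficacy result is shown for PP, print it beside ITT with the number excluded from PP for each reason.

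The cost is one clause and one definition. No extra visits or data are needed, since section 5.4 already asks for the closure date. The drawback is the upward selection described above: in the example with k = 3 and u = 10, PP goes from 70.2% to 72.0% against an ITT rate of 60.0%. The side-by-side display with exclusion counts makes that visible.

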#### **10.3.2. STUDIED PATIENTS / SUBJECTS**

##### **Disposition of patients / subjects**

The number of included patients, the number of patients who completed the planned medical visits and the number of patients who completed the overall study will be tabulated. The number of patients who discontinued prematurely the study will be also described.

Moreover, discontinued patients will be listed giving patient's number, age at inclusion, gender, last compression received, and reason for withdrawal and study duration.

A Subgroup analysis will be performed considering the ankle circumference (18-25cm group and 25-32cm group).

**Protocol deviations**; these will be listed by patient.

Moreover, the number of patients with at least one protocol deviation and the number of deviations will be tabulated by category and by term.

**Patients Demographic and other baseline characteristics** will be summarized using descriptive statistics. This analysis will be performed on Safety Population, ITT and PP populations (if different).

## **11. PROTOCOL MODIFICATIONS AND AMENDMENTS**

No modification of this protocol can be made without the agreement of the principal investigator.

Any substantial modification/amendment must be sent for approval to the Ethics Committee.

## **12. REGULATORY OBLIGATIONS AND ADMINISTRATIVE CONDITIONS**

In accordance with the principles of the Declaration of Helsinki (1964), revised in Tokyo (1975), Venice (1983), Hong Kong (1989), Somerset West (1996) and Edinburgh (2000), this investigation must be conducted according to Good Clinical Practices relative to the protection of individuals taking part in biomedical research. This may include an on-site audit and/or an inspection by representatives of the health authorities, at any time. The investigator must agree to the audit of the investigation's source documents by the representative of the health authorities

### **12.1. ETHIC COMMITTEE SUBMISSION**

The Ethics Committee must be informed of any protocol amendment and its approval must be obtained if the amendment is liable to significantly affect the safety conditions of the patients taking part in the research.

The present protocol, patient information sheet and patient consent form and other documents will be submitted by the Investigator to the relevant Research Ethics Committee for Gloucestershire Hospitals NHS Foundation Trust.

## **12.2. PATIENT INFORMATION AND WRITTEN AND INFORMED CONSENT**

The investigator will submit the patient information leaflet and written informed consent to the Ethics Committee for approval.

Signature of the consent forms must be obtained prior to patient enrolment in the study.

### **12.2.1. Patient Information Sheet**

Every patient meeting the selection criteria must be informed by the investigator of the aims of the research, its methodology and its duration, the constraints and foreseeable risks, along with the benefits that he/she may reasonably expect from his/her participation.

The main points of the information provided to the patient must be included in the information document that the Investigator gives the patient before the start of the investigation.

The patient must know:

- that he/she may refuse to take part in the research,
- that he/she is able to withdraw from the study at any time without prejudice,
- that he/she will not have to bear any additional financial costs as a result of his/her participation in the investigation.

The investigator must answer any additional questions asked by the patient about the investigation at the time of selection and throughout the duration of the research.

### **12.2.2. Patient's Consent Form**

Prior to inclusion in the investigation, the freely-given, express, informed consent of the patient must be obtained in writing in two originals. The patient keeps one copy and the investigator keeps the other.

## **12.3. PATIENT DATA**

### **12.3.1. Data collection**

The investigator must record the patients' individual data, independently of the Case Report Form.

The data must include identification of the patient, visit dates, information relative to vital signs, medical history, results of prescribed tests, any adverse events encountered or any other relevant comments. This information represents the "source data" (patient's medical file).

Any data recorded in the Case Report Form must also be present in the Source File (Patient Medical File).

The Case Report Form must be completed at the visits planned in the protocol.

The Consent Form must be placed in the patient's file throughout the investigation. Once the investigation has been completed, it must be placed in the Investigator's archive file, accompanied, at the end of the investigation, by a complete copy of the Case Report Form.

All original documents concerning laboratory data must be available in the patient files, since there is a possibility of errors or inaccuracies when transcribing original data into the Case Report Forms.

### **12.3.2. Information storage, archiving**

Any correspondence linked to the clinical investigation must be stored in the Investigator's archive file.

Information concerning patients, source documents, case report forms, approval of the Ethics Committee and correspondence relating to the investigation must be filed and stored in the archive file for 15 years by the Investigator, in accordance with European regulations.

## **13. STUDY SCHEDULE**

The investigators agree to comply with the following proposed schedule:

- September 2023: Initiation of the investigation,
- September 2024: End of the inclusion period,
- December 2024: End of the investigation,
- March 2025: Clinical Report of the trial.

***APPENDICES***

**APPENDIX (i)**

**URGO K2 Latex Free / URGO KTwo Latex Free**

The application of this medical device must be carried out by a person trained in the application of compression bandages. Read these instructions for use carefully.

 / **Urgo Medical**

Application video available.

## PRODUCT DESCRIPTION

**URGO K2/URGO KTwo** (or **URGO K2/URGO KTwo Latex Free**) is a two-layer multicomponent compression system, composed of a short stretch bandage and a long stretch bandage.

Its exclusive PresSure system technology, based on pressure indicators, guides application at the correct stretch and correct overlap, according to the selected kit.

## KIT CONTENTS

**URGO K2/URGO KTwo** is composed of KTech (Layer 1) and KPress (Layer 2).

**URGO K2/URGO KTwo Latex Free** is composed of KTech (Layer 1) and KPress Latex Free (Layer 2).

- Layer 1:

KTech: white, short-stretch bandage; provides compression, protection.

Composition: wadding: viscose, polyester; knitted layer: polyamide, elastane.

- Layer 2:

KPress/KPress Latex Free: pink/beige, cohesive long-stretch bandage; provides the additional compression necessary to achieve the therapeutic pressure and secures the bandages in place.

KPress composition: acrylic, polyamide, elastane; cohesive material containing natural latex.

KPress Latex Free composition: cotton, polyester, polyamide, elastane; synthetic latex free cohesive material.

## SIZES

**URGO K2/URGO KTwo** (or **URGO K2/URGO KTwo Latex Free**) is available in 2 sizes, for ankle circumferences: 18-25 cm and 25-32 cm.

**URGO K2/URGO KTwo** is available in 3 widths: 8 cm, 10 cm, and 12 cm.

**URGO K2 Latex free/URGO KTwo Latex Free** is available in 10 cm width only.

*(Some kit widths may not be available in your country.)*

## PROPERTIES

- Comfortable day and night for improved patient concordance.
- Easy to wear shoes.
- Good ankle mobility.

- Easy, fast, and accurate application thanks to the PresSure System: the therapeutic pressure is achieved from the first application.
- High level of compression at the ankle (around 40 mmHg).

- High SSI (Static Stiffness Index): Continuous pressure thanks to a high working pressure and a moderate resting pressure, creating a massage effect for improved venous return and oedema reduction.
- The system can stay in place up to 7 days.

## INDICATIONS

Treatment, in adults, of venous leg ulcer and/or lower limb oedemas where strong compression is recommended.

## CONTRAINDICATIONS

- Moderate or severe arterial conditions, notably with recent Ankle Brachial Pressure Index (ABPI) <0.8.
- Patients suffering from *phlegmatia coerulea dolens*, septic phlebitis.
- Oedema from congestive cardiac failure.
- Epifascial arterial bypass.
- Known hypersensitivity to any of the components – in particular latex for **URGO K2/ URGO KTwo**.

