### 4.3. EXCLUSION CRITERIA

#### **Related to the patient:**

- Patient participating in another clinical trial,
- Patient with known hypersensitivity to one of the components of the tested compression system Urgo KTwo Lite Latex free or the UrgoStart dressings,
- Patient who is unable to tolerate compression therapy,
- Patient presenting a neoplastic lesion treated by radiotherapy or chemotherapy or patients treated with immunosuppressive drugs or high-dose corticosteroids,
- Patient with a history of deep or superficial vein thrombosis in the 3 months prior to inclusion,
- Patient confined to bed.

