## **5.2. INCLUSION VISIT: DAY 0**

Any patient presenting with a new venous leg ulcer (less than six weeks duration) and meeting all the selection criteria may be approached for inclusion in the study irrespective of previous local treatment for his chronic wound.

The patient must be informed of the nature of the study for which he/she is being selected and must sign a written informed consent form in duplicate, prior to any investigation relative to this study.

The investigator then considers that the patient is included in the investigation and must therefore document the Case Report Form.

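### The entry criteria omit two contraindications of the study bandage, cardiac oedema and epifascial bypass, so a patient barred from the bandage can be included

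*Protocol*

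**What the plan says.** Appendix (i), under Contraindications, has five bullets for the compression system. Two of them are "Oedema from congestive cardiac failure" and "Epifascial arterial bypass".

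Eligibility is set in Sections 4.2 and 4.3. The items closest to these two conditions are:

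- the ABPI limit of 0.85, stated as an inclusion criterion and again as an exclusion;
- the exclusion "Patient who is unable to tolerate compression therapy";
- the exclusion for a "history of deep or superficial vein thrombosis in the 3 months prior to inclusion".

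No criterion mentions heart failure, oedema of cardiac origin or a bypass, and none refers to device contraindications in general.

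Section 5.2 says that a patient with a new venous ulcer "meeting all the selection criteria may be approached for inclusion in the study". Section 5.1 adds, after consent, that "once all inclusion and exclusion criteria are met, patients will be included in the study", and that "Patients will be allocated to the Urgo K2 compression system". The same section requires both devices to be used following the manufacturers' "recommendations as described in the respective device monographs", which brings the contraindications of Appendix (i) into the protocol by reference.

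**The concern.** The protocol has two rules that disagree for a small group of patients. The entry rule lets them in and assigns the bandage. The application rule, through the appended instructions, forbids it. No step before inclusion resolves the conflict. The protocol relies on the investigator or the person applying the bandage to recall the instructions at the first application.

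Two outcomes are possible:

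- **The contraindication is missed.** A system that delivers about 40 mmHg at the ankle and may stay on for up to 7 days (Appendix (i), Properties) is applied to a patient in whom the manufacturer bars it. This is the main consequence.
- **It is noticed after inclusion.** The patient is in the trial but cannot receive the study procedure. Without it, the patient falls outside both the ITT and the Safety populations of Section 10.3.1.

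**Working it through.** No calculation in the protocol bears on this point. The check sets the five contraindication bullets of Appendix (i) against every criterion in Sections 4.1 to 4.3.

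| Contraindication (Appendix (i)) | Nearest criterion (Sections 4.1–4.3) | Match |
|---|---|---|
| Moderate or severe arterial disease, notably ABPI below 0.8 | ABPI limit of 0.85 | Partial: the ABPI element is covered, and more strictly; arterial disease not shown by ABPI is not named |
| Phlegmatia coerulea dolens, septic phlebitis | Vein thrombosis in the previous 3 months | Partial |
| Cardiac oedema | None | None |
| Epifascial bypass | None | None |
| Hypersensitivity to a component | Hypersensitivity exclusion | Direct in substance |

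Tally: 1 direct + 2 partial + 2 none = 5. This is a reading of the text, not a statistic.

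Next, could any existing provision close the two open rows?

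1. **ABPI.** The threshold does not ask about a bypass, so a patient with a bypass and an ABPI above 0.85 passes. Appendix (i) treats the matter separately: under Precautions of use it recommends a fuller vascular work-up where there has been revascularisation.
2. **Intolerance of compression.** This concerns whether the patient can bear the bandage. A patient may tolerate a bandage that is contraindicated.
3. **Venous diagnosis.** A duplex-confirmed venous ulcer does not rule out coexisting cardiac oedema or a bypass.
4. **Day 0 data.** Section 5.2 collects comorbidities, surgical history, pulses and ABPI. The information is relevant, but no entry rule acts on it.
5. **Precautions of use.** Appendix (i) permits the system in cardiac failure or arterial bypass generally, after referral to a specialist and with close supervision. That does not lift the two specific bars listed under Contraindications.
6. **Timing.** In the schedule of Appendix (ix), validation of the exclusion criteria is marked at Day 0 only. As Section 4.3 stands, that check does not cover these two conditions.

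Size of the analysis effect: each included patient who does not receive the study procedure is 1/60 = 1.7% of the planned sample. Section 10.1 plans no statistical tests, so none is affected.

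**The case against.** The strongest reply is that the protocol already forbids the harmful act. Section 5.1 makes the manufacturer's instructions mandatory, so bandaging such a patient would breach the protocol, and all that is missing is a repeat of the bar at entry. The study runs in a specialist leg ulcer service, the relevant history is taken at Day 0, and Appendix (i) requires a trained applier. The GP letter in Appendix (vii) also asks the GP to say if there is a reason against participation. Several failures would be needed before harm occurred.

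Much of this is fair and limits the weight of the point. These safeguards, however, act at or after application, or gather data that no eligibility rule uses; the GP letter is written once the patient has agreed. Section 4.3 already turns other device limits into entry criteria (hypersensitivity, and arterial status through ABPI), so the transfer of the contraindications is incomplete.

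Three further objections stand in part:

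- The arterial row could be read as covered rather than partial. The two rows with no match do not depend on it.
- Community staff deliver care between visits and only the centre may change treatment (Appendix (vi)). That adds little for a condition present at baseline, where the first application is decisive, and an entry criterion gives no protection against cardiac oedema that develops later.
- The protocol lists no specific cardiac assessment, so attributing oedema to the heart remains a clinical judgement.

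**Conclusion.** The concern holds. Two of the five contraindications of the study bandage have no counterpart in the eligibility criteria, and the entry rule as written can admit and assign to Urgo K2 a patient whom the incorporated instructions bar from it. The conflict arises only through the Section 5.1 reference to those instructions; no text directs that such a patient be bandaged in defiance of them.

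The importance is patient safety at entry. The documents do not give the number of patients affected, which is assumed to be small. The loss to the analysis is minor, at 1.7% of the planned sample per patient, and would be visible in the disposition table of Section 10.3.2. The interpretation of the primary endpoint is not shown to change. The change is worth making because it is cheap and moves the check to before inclusion.

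**What to change.** Add one exclusion to Section 4.3 that names cardiac-failure oedema and epifascial arterial bypass and extends to any other contraindication in the appended device instructions. The general clause also closes the two partly matched rows.

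Check it at Day 0 with the other exclusion criteria, using the medical and surgical history and the vascular assessment already recorded there. The cause of the oedema stays a matter for the investigator's judgement, now exercised before inclusion. State that patients who fall only under the Precautions of use remain eligible, subject to the specialist referral and close monitoring set out there.

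The cost is one line of text and one item in the existing Day 0 check. No new examination is prescribed. The eligible pool narrows slightly, by patients who should not receive this bandage in any case.
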